1.	List of Abbreviations	4
2.	Introduction.....	4
3.	Study Design	4
4.	Study Objectives.....	6
5.	Study Endpoints.....	6
5.1	Primary Endpoint(s)	6
5.2	Safety Endpoint(s).....	6
6.	Statistical Considerations	7
6.1	Determination of Sample Size.....	7
6.2	Randomization	7
6.3	Interim Analysis.....	7
7.	Statistical Analysis	7
7.1	General	7
7.2	Analysis Populations.....	8
7.3	Handling of Missing, Incomplete and Repeat Data	8
7.4	Derived Data	9
7.5	Baseline Data	10
7.6	Disposition Data.....	11
7.7	Protocol Deviations	12
7.8	Multiplicity	12
7.9	Analysis of Primary Endpoint(s)	12
7.10	Changes in Analysis Methods Specified in the Protocol.....	14
8.	References.....	15

CONFIDENTIAL AND PROPRIETARY

This document contains information that is confidential and proprietary to Smith & Nephew PLC and Smith & Nephew, Inc. and is intended for use only by Smith & Nephew and its manufacturer. It shall not be reproduced or copied in whole or in part, nor shall the contents be disclosed by any means without prior written permission from Smith & Nephew, nor shall anyone make any use of it that is contrary to the expressed or implied wishes of Smith & Nephew

Statistical Analysis Plan	Smith+Nephew
A Prospective, Non-randomized, Multi-Center Investigation of All-suture-based Repair of Horizontal Meniscal Tears (STITCH Study)	Number: CTX-CP001
	Version: 1, 4-Sept-2019
	Page: 4 of 15

1. List of Abbreviations

Abbreviation	Definition
ADL	Activities of Daily Living (KOOS)
IKDC	International Knee Documentation Committee
KOOS	Knee Disability and Osteoarthritic Outcome Score
QOL	Quality of Life (KOOS)
S&N	Smith & Nephew Inc.
SAP	Statistical Analysis Plan
TFL	Tables, Figures, and Listings

2. Introduction

The following Statistical Analysis Plan (SAP) details the statistical considerations, including the data analysis methods, for the Study Protocol CTX-CP001 (14th-Dec-2014). Related documents to this SAP are the Study Protocol, Case Report Form (CRF), and Tables, Figures and Listings (TFL) Templates Shells. The statistical analyses specifications presented herein will thus form the basis of the 2-year final study report.

3. Study Design

The study is an interventional trial designed as a non-randomized, single-arm, open-label study of horizontal repairs of the meniscus tears using commercially available products. The study was designed to enroll 30 subjects at up to 10 investigational sites in the United States.

Table 3.1 shows the planned visit schedule.

CONFIDENTIAL AND PROPRIETARY

This document contains information that is confidential and proprietary to Smith & Nephew PLC and Smith & Nephew, Inc. and is intended for use only by Smith & Nephew and its manufacturer. It shall not be reproduced or copied in whole or in part, nor shall the contents be disclosed by any means without prior written permission from Smith & Nephew, nor shall anyone make any use of it that is contrary to the expressed or implied wishes of Smith & Nephew

Statistical Analysis Plan	Smith+Nephew
A Prospective, Non-randomized, Multi-Center Investigation of All-suture-based Repair of Horizontal Meniscal Tears (STITCH Study)	Number: CTX-CP001
	Version: 1, 4-Sept-2019
	Page: 5 of 15

Table 3.1. Study Visit Schedule

STUDY ACTIVITY SCHEDULE							
Activity	Visit 1	Visit 2	Visit 3	Visit 4	Visit 5	Visit 6	Visit 7
	Screen < 4 weeks	Procedure	7-15 Days	90 Day ±7 days	185 Day ±14 days	365 Day ±30 days	730 Day ±30 days
Informed consent	X						
Screening Inclusion / Exclusion	X						
Demographics / Medical History	X						
Radiographs	X ^{1,5}						X ¹
MRI	X ⁵					X ²	
Images		X ³					
Arthroscopy Inclusion / Exclusion		X					
Study Procedure		X					
Details of Procedure		X					
Details of Pathology		X					
Safety Follow-Up			X	X	X	X	X
KOOS	X			X	X	X	X
IKDC Subjective	X			X	X	X	X
Lyshlom	X			X	X	X	X
Tenger	X			X	X	X	X
In-office Arthroscopy					X⁴		

¹Standing AP X-ray

²MRI 1.5 T or greater, no contrast to be reviewed by independent radiologist appointed by sponsor.

³Video, still photographs and diagrams of procedure.

⁴If available.

⁵ Within 6 months of Procedure

CONFIDENTIAL AND PROPRIETARY

This document contains information that is confidential and proprietary to Smith & Nephew PLC and Smith & Nephew, Inc. and is intended for use only by Smith & Nephew and its manufacturer. It shall not be reproduced or copied in whole or in part, nor shall the contents be disclosed by any means without prior written permission from Smith & Nephew, nor shall anyone make any use of it that is contrary to the expressed or implied wishes of Smith & Nephew

Statistical Analysis Plan	Smith+Nephew
A Prospective, Non-randomized, Multi-Center Investigation of All-suture-based Repair of Horizontal Meniscal Tears (STITCH Study)	Number: CTX-CP001
	Version: 1, 4-Sept-2019
	Page: 6 of 15

4. Study Objectives

The primary objectives of this study are to assess reoperation rate, improvements in knee pain and function, and meniscus repair rate following all-suture-based repair of the horizontal meniscal tear.

5. Study Endpoints

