Reparability and healing potential are not identical; however the concepts are often used interchangeably. One term is correctly applied to the technical feasibility of performing a repair and maintaining the repair integrity over time; the other is a biologic phenomenon. The current teaching regarding horizontal/oblique and tears is that they are most often irreparable.^{32,33,34,35,36} As such, little clinical documentation regarding the feasibility of repairing these tears exists. Furthermore, contrary to clinical doctrine, the scant existing literature on the subject challenges the understanding of the healing potential of horizontal/oblique tears by suggesting that repair has successful outcomes anywhere from 50-100% of the time.^{37,38,39,40,41,42,43,44} Clearly additional prospective assessments of horizontal/oblique tears is needed.

Horizontal tears are notable for a few reasons: 1) they are common, comprising up to 20% of meniscus tears^{45,46,47}; 2) despite improvements in meniscal repair methods, the techniques have been difficult to employ successfully across these particular tears. With newer suture delivery methods enabling surgeons to more easily place sutures in patterns that reduce these tears, it is possible to further assess and document their reparability. This study will begin that process by examining and documenting the ability to successfully repair horizontal meniscus tears using all suture based techniques.

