3.2. Rationale and Justification for the Study

a. Rationale for the Study Objectives

Although the clinical consensus holds that horizontal tears are often irreparable, there are no prospective, multi-center trials in the literature that document successful repair of the meniscus, surgical reoperation rates for meniscal tears and improvements in knee pain and function.

b. Rationale for Study Population

The study is limited to healthy subjects with horizontal meniscal tears. Although these injuries can occur in any age group, slightly younger age range (18-60 years of age) allows inclusion of knees with less likelihood of significant arthritic changes

which may mask measurement of knee pain and function improvements following the treatment procedure.

c. Rationale for Study Design

It is well established in the literature that meniscectomy leads to increased risk of late osteoarthritis, and conversely, that repairing the meniscus reduces this risk. The clinical consensus is that preservation of meniscal tissue should be the goal whenever possible. The alternative for these patients is meniscectomy (a failure endpoint in this study), therefore there is no available control. A prospective, non-randomized, single-arm assignment study design is the best method for obtaining objective data for clinicians and patients in weighing the viability of meniscal repair versus primary meniscectomy.

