4. STUDY DESIGN

4.1. Hypotheses

No formal hypotheses testing will be done. However, primary outcome measures that will be examined include: A substantial proportion of the subjects will show meniscus healing at 6 months. The two-year reoperation survival rate will be similar or less than historical rates. Patient reported outcomes will be improved at six-months following the procedure.

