4.3. Objectives

The primary objectives of this study are to assess reoperation rate, improvements in knee pain and function, and meniscus repair rate following all-suture-based repair of the horizontal meniscal tear.

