4.5. Study Assessments

For timing of study assessments activities and visit windows see Section 14.

a. Outcome Assessments

- International Knee Documentation Committee Subjective Knee Evaluation Form (IKDC Knee Evaluation)
- Knee Injury and Osteoarthritis Outcome Score (KOOS)
- Lysholm Knee Questionnaire
- Tenger Activity Scale
- In-office needle arthroscopy assessment of meniscus repair (when performed)

- Freedom from reoperation on the index meniscus repair site;
- Condition of meniscal tissue per MRI (Appendix 7);
- Joint condition per X-ray (Appendix 7).

b. Safety Variable (see Section 7.1 for definitions)

- Safety follow-up

c. Patient and Procedural Variables

- Patient demographics and knee pathology history
- Details of procedure
- Details of tear

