All subjects will be evaluated, and a safety follow-up form will be completed. In addition all subjects will complete the following:

- KOOS

- IKCD Knee Evaluation
- Lysholm Knee Questionnaire
- Tegner Activity Scale

Where available, subjects will undergo an in-office arthroscopy (i.g. VisonScope) to assess the tissue repair. Clinical follow-up should continue with or without the arthroscopy.

f. Fourth Follow-up [365 Day \pm 30 days] (Study Visit 5)

All subjects will be evaluated, a safety follow-up form will be completed and an MRI will be performed. In addition all subjects will complete the following:

- KOOS
- IKCD Knee Evaluation
- Lysholm Knee Questionnaire
- Tegner Activity Scale

g. Fifth Follow-up [730 Day \pm 30 days] (Study Visit 6)

All subjects will be evaluated, a safety follow-up form will be completed and a Standing AP x-ray will be obtained for evaluation of joint space narrowing. In addition all subjects will complete the following:

- KOOS
- IKCD Knee Evaluation
- Lysholm Knee Questionnaire
- Tegner Activity Scale

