15. LIST OF ATTACHMENTS

Appendix 1	ISAKOS Criteria
Appendix 2	Cartilage Guidance
Appendix 3	Modified Outerbridge Scale
Appendix 4	Kellgren-Lawrence Grading Scale
Appendix 5	Subject Informed Consent Form
Appendix 6	Case Report Forms
	
• 001 Screening Inclusion Exclusion• 002 Demographics and History• 003 Arthroscopy Inclusion Exclusion• 004 Details of Pathology• 005 Details of Procedure• 006 Safety Follow-Up• 007 Complication• 008 Details of Reoperation• 009 Study Completion• 010 Protocol Deviation• 011 Data Clarification• 012 KOOS• 013 IKDC Subjective Knee Evaluation• 014 Lysholm Knee Questionnaire• 015 Tegner Activity Scale• 016 Meniscus Repair Assessment
Appendix 7	Imaging Guidance

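### Six-month meniscus healing is a protocol primary outcome measure with no analysis in the visible SAP, and the primary objective of a meniscus repair rate is never defined

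*SAP*

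**What the plan says.** SAP section 4 names three primary objectives: "The primary objectives of this study are to assess reoperation rate, improvements in knee pain and function, and meniscus repair rate following all-suture-based repair". Protocol 4.3 names the same three, the last being "meniscus repair rate following all-suture-based repair of the horizontal meniscal tear". The rationale in Protocol 3.2 makes the same three-way split, saying that no prospective multi-center trials "document successful repair of the meniscus, surgical reoperation rates for meniscal tears and improvements in knee pain and function".

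Protocol 4.1 rules out formal hypothesis testing but lists primary outcome measures to be examined. The first is: "A substantial proportion of the subjects will show meniscus healing at 6 months".

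The protocol provides a way to observe this. Section 4.5 lists among its outcome assessments "In-office needle arthroscopy assessment of meniscus repair (when performed"). Section 6.2 says that at the Day-185 follow-up, where available, "subjects will undergo an in-office arthroscopy (i.g. VisonScope) to assess the tissue repair". The list of attachments includes a form titled "016 Meniscus Repair Assessment".

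SAP 5.1 gives as primary endpoints freedom from reoperation, KOOS, IKDC, Lysholm and Tegner. SAP 7.4 and 7.9 derive and analyse those. In the visible SAP, the Day-185 arthroscopy appears only in the visit schedule (Table 3.1).

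**The concern.** There are two gaps, and they differ in firmness.

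The firm one is healing. The protocol calls it a primary outcome measure and schedules an assessment at the matching time, but the visible SAP has no healing endpoint, derived variable or summary. SAP section 2 makes these specifications the basis of the 2-year final report, so a report that follows them would say nothing on healing.

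The second is an undefined term. Without a definition of meniscus repair rate, nobody can tell whether that primary objective has been met. If the meaning, the healed rule or the denominator is chosen after the data are known, the choice is open to selection.

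Freedom from reoperation cannot stand in for healing, because a repair that has not healed may never be reoperated.

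**Working it through.** The plan states no healing figure, so there is nothing to reproduce. The check is a reconciliation of text, followed by an illustration of precision.

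**Step 1: is healing analysed anywhere in the visible SAP?**
- 5.1: reoperation and four patient-reported instruments. No healing item.
- 7.4: populations, study duration, freedom from reoperation, score changes, time since injury, time to reoperation, MCID indicators and adverse event variables. Repair status appears in one formula, but that formula sits under freedom from reoperation and does not measure healing.
- 7.5 and 7.6: baseline, surgical and disposition summaries. No healing.
- 7.9: freedom from reoperation, reoperations and patient-reported scores. No healing.
- 7.10 as visible: safety only.

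**Step 2: what could meniscus repair rate mean, and is it served?**
- *Healing.* Not served (step 1).
- *Technical reparability.* Protocol 3.1 supports this reading, since it speaks of "examining and documenting the ability to successfully repair horizontal meniscus tears using all suture based techniques". SAP 7.6 gives the numbers and percentages screened and entered. Because Protocol 6.2 enrols a subject only once the repair is completed, the percentage entered among those screened is a crude technical rate, although those screened include ineligible patients. Among enrolled subjects the rate is 100% by construction.
- *Durability.* Protocol 3.1 separates reparability from biological healing and counts lasting integrity of the repair under reparability. Freedom from reoperation at 6 months, 1 year and 2 years partly serves this.

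**Step 3: how informative could a healing rate be?**

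From SAP 6.1: 30 accrued, 3 excluded from all analyses, 30 − 3 = 27. Everything else is assumed: m subjects assessed at Day 185, h of them healed (two thirds throughout), and r unassessed subjects reoperated at the index site before Day 185 and counted as not healed.

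- Clopper-Pearson 95% limits: lower = Beta quantile 0.025 with parameters (h, m − h + 1); upper = Beta quantile 0.975 with parameters (h + 1, m − h).
- Bounds over N treated: low = h/N; high = (h + N − m − r)/N.

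| N | m | h | r | Healed among assessed (95% CI) | Low bound | High bound |
|---|---|---|---|---|---|---|
| 27 | 9 | 6 | 0 | 67% (29.9 to 92.5) | 6/27 = 22.2% | 24/27 = 88.9% |
| 27 | 18 | 12 | 0 | 67% (41.0 to 86.7) | 12/27 = 44.4% | 21/27 = 77.8% |
| 27 | 24 | 16 | 0 | 67% (44.7 to 84.4) | 16/27 = 59.3% | 19/27 = 70.4% |
| 27 | 18 | 12 | 2 | 67% (41.0 to 86.7) | 12/27 = 44.4% | 19/27 = 70.4% |
| 30 | 18 | 12 | 0 | 67% (41.0 to 86.7) | 12/30 = 40.0% | 24/30 = 80.0% |

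With 18 of 27 assessed and r = 0, the bounds are 9/27 = 33 points apart. With 24 assessed they are 3/27 = 11 points apart. The number assessed therefore matters as much as the healed proportion, and it has to be reported.

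**The case against.** The best defence is that the SAP follows the protocol's own endpoint list. The synopsis endpoints are freedom from reoperation and the four patient-reported scales, and its objectives speak of documenting the repair, which the surgical summaries in SAP 7.5 do. Protocol 9.2 names no healing analysis either. This stands: the conflict is inside the protocol, with 4.1 and 4.3 on one side and the synopsis and 9.2 on the other. It does not close the gap, because the SAP restates repair rate as a primary objective and the healing measure in 4.1 remains unanswered.

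A reader might infer that the SAP dropped an endpoint the protocol had formally set, or that no meaning of repair rate is served. The documents support neither. Healing is absent from the synopsis endpoints, and the reparability and durability readings are each partly covered.

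Three further cautions hold:
- The SAP contents list a section 7.10 on changes in analysis methods from the protocol. The visible 7.10 is safety, and the listed section's text is not visible. It might explain the omission.
- The link between CRF-016 and the Day-185 arthroscopy rests on the form's title. Protocol 6.2 ties CRF-004 and CRF-005 to their procedures but does not mention CRF-016, and the form's content is not seen.
- The study is descriptive and the arthroscopy optional, so an elaborate analysis is not called for. That limits the remedy to a count and a proportion, but does not justify reporting nothing.

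**Conclusion.** The point holds, as something that should be fixed, with medium confidence. On the visible text, 6-month healing is a stated primary outcome measure with a scheduled, optional assessment and no analysis. Separately, meniscus repair rate is a primary objective without a definition. The fault is a missing definition and summary, not missing power, since no formal test is planned.

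The size in real data cannot be known, because the documents give no counts of subjects assessed or healed. Under the assumed case of 12 healed among 18 assessed, the interval of 41.0% to 86.7% and the bounds of 44% to 78% over 27 subjects show a result that is imprecise but still informative. The conclusion would change if the unseen SAP section on changes from the protocol, or the unseen forms and appendices, define the term or give a reason for leaving healing out.

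**What to change.** In SAP 5.1, 7.4 and 7.9, add a descriptive 6-month healing analysis from the Day-185 arthroscopy data, presumably recorded on CRF-016:
- Report the numbers treated, assessed and healed, and the proportion healed among those assessed with a Clopper-Pearson 95% interval, the method SAP 7.9 already uses.
- Show separately the subjects not assessed and those reoperated at the index site before Day 185. Say whether the 3 subjects excluded in SAP 6.1 count as treated.
- Fix the healed/not-healed rule before the forms are tabulated, or label it post hoc.
- Best-case and worst-case bounds over all treated subjects are a useful optional addition.

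Also state which meaning of meniscus repair rate is intended, or remove it from the primary objectives with a reason. If it means technical completion, say that it is 100% among enrolled subjects by construction; the healing measure in Protocol 4.1 still needs its own summary.

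The cost is SAP wording and one table, with no new visits, procedures or subjects, though a healed rule may have to be written if the form has none. The downside is that, with optional arthroscopy, the estimate may be wide, the assessed subjects may be unrepresentative, and the result may look less favourable than freedom from reoperation.

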5.1 Primary Endpoint(s)

The primary endpoints include:

- Freedom from reoperation of the index meniscus repair site at 6 months, 1 year, and 2 years;
- Improvements in knee pain and function as measured by KOOS
- IKDC Knee evaluation,
- Lysholm Knee scale, and
- Tegner Activity Scale

5.2 Safety Endpoint(s)

Safety follow-up includes reporting of a:

Complication

A complication is any untoward medical occurrence, unfavorable and unintended sign (including clinically significant abnormal laboratory finding), symptom, or condition experienced by the subject and temporally associated with the procedure whether or not considered related to the procedure.

Major Complication

Any complication attributable to the meniscal repair procedure that, in the view of either the Investigator or Sponsor, results in any of the following outcomes:

- Death;
- Life-threatening illness or injury;
- Inpatient hospitalization or prolongation of existing hospitalization;

CONFIDENTIAL AND PROPRIETARY

This document contains information that is confidential and proprietary to Smith & Nephew PLC and Smith & Nephew, Inc. and is intended for use only by Smith & Nephew and its manufacturer. It shall not be reproduced or copied in whole or in part, nor shall the contents be disclosed by any means without prior written permission from Smith & Nephew, nor shall anyone make any use of it that is contrary to the expressed or implied wishes of Smith & Nephew

Statistical Analysis Plan	Smith+Nephew
A Prospective, Non-randomized, Multi-Center Investigation of All-suture-based Repair of Horizontal Meniscal Tears (STITCH Study)	Number: CTX-CP001
	Version: 1, 4-Sept-2019
	Page: 7 of 15

- Persistent or significant incapacity or substantial disruption of the ability to conduct normal life functions;
- Important medical events that, based upon appropriate medical judgment, require medical or surgical intervention to prevent one of the above outcomes.

6. Statistical Considerations

6.1 Determination of Sample Size

There was no formal sample size calculation carried out for this clinical observational study because the study was not planned to test any formal hypothesis. Prior to the study commencement, it was planned to enroll 30 subjects into the study, and the sample size was accrued. However, a total of 3 subjects were excluded from all analyses for having met protocol deviations.

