1. ABBREVIATIONS, ACRONYMS AND DEFINITIONS

All Suture-Based Technique: A repair technique (all-inside, inside-out, outside-in or combination thereof) utilizing only suture without implanting any other material intended to anchor and/or replace suture material.

BMI: Body Mass Index

Complex Tear: Multiple discreet tears, tears with multiple planes, or meniscal tissue incapable of holding suture.

Consented Patient: A patient who, after the screening process, grants consent to participate in the trial.

CFR: Code of Federal Regulations

CRF: Case Report Form; includes all study forms.

Enrolled Subject: A patient who has been consented, meets all criteria for inclusion immediately prior to treatment and receives all suture-based repair of meniscal tear.

HT: Horizontal tear (of the meniscus); the majority of the tear is oriented primarily (but not exclusively) parallel to the plane of knee joint dividing the structure into superior and inferior flaps. For the purpose of this protocol, HT includes obliquely-oriented tears. These tears may open at the central apex or along the inferior surface of the meniscus. Some horizontal tears may have a radial component (bird beak) in the central White Zone.

HIPAA: Health Insurance Portability and Accountability Act

IKDC: International Knee Documentation Committee

IRB: Institutional Review Board

ISAKOS: International Society of Arthroscopy, Knee Surgery and Orthopaedic Sports Medicine

KOOS: Knee injury and Osteoarthritis Outcome Score

PCL: Posterior Cruciate Ligament

Protocol Deviation: A protocol deviation is any change, divergence, or departure from the study design or procedures of a research protocol that is under the Investigator's control and that has not been approved by the IRB.

Protocol Violation: A protocol violation is a deviation from the IRB-approved protocol that may affect the subject's rights, safety, or well-being and/or the completeness, accuracy and reliability of the study data.

Red Zone: The well-vascularized peripheral-most ~30% of the meniscus.

Red-White Zone: The transition between the outermost and innermost portions of the meniscus where vascularity diminishes from peripheral to central.

Subject: A consented patient who has been enrolled in the study.

White Zone: The inner (avascular) one-third of the meniscus.

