Investigator-specific standard-of-care arthroscopy will be performed. Intraoperative eligibility criteria will be evaluated. If **all** of the arthroscopy inclusion criteria are met and **none** of the arthroscopy exclusion criteria are met, the subject will be eligible for study enrollment. The subject is officially enrolled in the trial when the meniscal repair is completed.

Meniscal Repair Procedure

The Investigator will follow standard all-inside and/or inside-out, and/or outside-in, and/or NovoStitch arthroscopic procedures:

- Recommended spacing of sutures is 5mm;
- Video, still photographs and diagrams of the arthroscopy procedure will be captured for documentation of meniscal tear, tear preparation and tear treatment parameters. Images and diagrams will be provided to the sponsor. All patient identifying information should be removed prior to transferring images to the sponsor.

The ISAKOS Questionnaire documenting details of the meniscus tear and required excision (if any) will be completed (CRF-004, Details of Pathology). Details of the procedure will be documented (CRF-005, Details of Procedure) will be completed. It contains questions regarding the following:

- Number and configuration of sutures used;
- Repair technique and instruments;
- Meniscal repair time recorded from intraarticular introduction of suture to transection of final suture knot;
- Other intraoperative findings.

Rehabilitation Procedure

All subjects will follow their Investigator's preferred rehabilitation plan based on the particular tear and repair characteristics. At a minimum, all subjects must meet the following post-operative thresholds:

- Weight bearing as tolerated
- Hinged knee brace locked in extension when walking (4-6 weeks), released to 90 degrees for sitting/driving
- No squatting or stand up/sit down motions until after 6 weeks post-op
- No cutting or pivot sports until after 6 months post-op

c. First Follow-up [7-15 days] (Study Visit 3)

Subjects will be evaluated and a safety follow-up will be completed.

d. Second Follow-up [90 Day \pm 7 days] (Study Visit 4)

All subjects will be evaluated and a safety follow-up form will be completed. In addition all subjects will complete the following:

- KOOS
- IKCD Knee Evaluation
- Lysholm Knee Questionnaire
- Tegner Activity Scale

e. Third Follow-up [185 Day \pm 14 days] (Study Visit 4)

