9. STATISTICAL PLAN

9.1. Subject Population(s) for Analysis

Data obtained from all enrolled subjects will be analyzed on a per-treatment (PT) basis, which will include all enrolled subjects who receive the protocol-defined treatment of suture-based meniscal repair.

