7.2 Analysis Populations

Safety Population (SAF): all subjects who receive study treatment. This population include all enrolled subjects who receive the protocol-defined treatment of suture-based meniscal repair. This will be used for summaries of disposition of the subjects, protocol deviations/violations, and safety.

Analysis Population (AS): all SAF subjects with no significant protocol deviations, meet the inclusion/exclusion criteria, and did not withdraw early (except for closure at any time). This population will be used for supportive evidence of the primary variable.

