The patient reported outcomes (IKDC, KOOS Pain, KOOS Symptom, KOOS ADL, KOOS Sport, KOOS QOL, Lysholm, Tegner) will be summarized at each visit using descriptive characteristics for continuous variables (i.e. mean, median, SD, minimum, and maximum values). In addition, changes from baseline (Study Visit 1) to the subsequent follow-up visits will be similarly summarized. Results will be presented in narrative and graphically.

These measures will also be analyzed using inferential statistics. As appropriate, a repeated measure ANOVA or Wilcoxon signed rank test will be completed for each outcome measure. If a significant trend is identified, significance among time points, especially preoperative measures, may be further explored using the appropriate pair-wise comparisons. In all cases a p value equal to or less than 0.05 will be considered significant. Ninety-five percent (95%) CIs will be presented as well as corresponding p-values from the pair-wise comparisons of means from baseline to planned visits of interest (i.e. from Study Visit 1 to Day 90, Day 185, Day 365, and Day 730).

In addition, for Lysholm and/or IKDC, the numbers and proportions of subjects (out of total number of subjects providing data), together with a 95% confidence interval (calculated using the Clopper-

CONFIDENTIAL AND PROPRIETARY

This document contains information that is confidential and proprietary to Smith & Nephew PLC and Smith & Nephew, Inc. and is intended for use only by Smith & Nephew and its manufacturer. It shall not be reproduced or copied in whole or in part, nor shall the contents be disclosed by any means without prior written permission from Smith & Nephew, nor shall anyone make any use of it that is contrary to the expressed or implied wishes of Smith & Nephew

Statistical Analysis Plan	Smith+Nephew
A Prospective, Non-randomized, Multi-Center Investigation of All-suture-based Repair of Horizontal Meniscal Tears (STITCH Study)	Number: CTX-CP001
	Version: 1, 4-Sept-2019
	Page: 14 of 15

Pearson Exact method ⁱⁱⁱ, meeting the minimal clinically important differences (MCIDs) from baseline to Days 185 and 365 (MCID185_{IKDC}=6.3, MCID365_{Lysholm} =10.1, MCID365_{IKDC}=16.7) will be presented. There was no MCID for Lysholm at Day 185.

7.10 Analysis of Safety Endpoints:

All safety analyses and summaries will be done using the Safety Population.

The safety analyses will summarize the number (n) and percentages (%) of:

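### SAP 6.1 drops 3 of the 30 accrued subjects from every analysis, against the all-treated Safety Population in SAP 7.2 and 7.10 and the analysis set in protocol 9.1

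*SAP*

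**What the plan says.** SAP 6.1 says that 30 subjects were planned and that this number was reached. It continues: "However, a total of 3 subjects were excluded from all analyses for having met protocol deviations". It does not say what the deviations were, whether the 3 had the repair, or when the decision was taken.

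SAP 7.2 defines two sets.

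- The first is "Safety Population (SAF): all subjects who receive study treatment". A second sentence describes this set as enrolled subjects given the protocol-defined suture repair. On its use, the SAP says: "This will be used for summaries of disposition of the subjects, protocol deviations/violations, and safety". SAP 7.10 (Analysis of Safety Endpoints) repeats the rule: "All safety analyses and summaries will be done using the Safety Population".
- The second, the Analysis Population, takes the Safety Population and removes subjects with significant deviations, eligibility failures or early withdrawal. Of this set the SAP says: "This population will be used for supportive evidence of the primary variable".

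Protocol 9.1 specifies one per-treatment set, "which will include all enrolled subjects who receive the protocol-defined treatment of suture-based meniscal repair". It has no exclusion for deviations.

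Two protocol statements fix who counts as enrolled. Section 6.2 (Surgery and Rehabilitation) says: "The subject is officially enrolled in the trial when the meniscal repair is completed". The definition of an enrolled subject in section 1 is a consented patient who "meets all criteria for inclusion immediately prior to treatment and receives all suture-based repair of meniscal tear".

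**The concern.** The exclusion in SAP 6.1 is unqualified, so it reaches the safety, disposition and deviation summaries as well as the efficacy results. The sections that define the analysis sets do not allow for it. A programmer working from this SAP cannot tell whether the starting denominator for complications is 27 or 30.

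Followed literally, 6.1 has three effects:

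- Any complications in the 3 subjects disappear from the safety tables.
- The 3 are missing from the deviation summary in SAP 7.7, although deviations are the reason they were removed.
- The primary reoperation result is computed without them, although protocol 9.1 would include them if they had the protocol-defined repair.

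The study has one arm and no control, so these proportions and their intervals are its main reoperation result. A reader could not see whether that result depends on the exclusion.

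The trial is open label, and the exclusion is reported as already done in a version 1 SAP dated 4 September 2019. Knowledge of outcomes at the time of the decision therefore cannot be ruled out. Nothing in the documents shows it.

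**Working it through.** **Step 1: what each section implies for the 3 subjects.** The deviations are not described, so each possibility is taken in turn.

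- *They had the protocol-defined repair and were eligible.* They are enrolled (protocol 1 and 6.2), in the Safety Population (SAP 7.2) and in the protocol 9.1 set. SAP 6.1 contradicts all of these.
- *They were repaired but failed an eligibility criterion.* They satisfy the first sentence of the Safety Population definition, so 6.1 still conflicts with 7.2 and 7.10 on that sentence. By the protocol 1 definition they were not enrolled, so the accrual of 30 is overstated. By protocol 6.2, completing the repair would suggest that they were.
- *They were treated, but not with the protocol-defined repair.* They may fall outside protocol 9.1 and the second Safety Population sentence. They also fall outside the enrolment definition, so 30 were not accrued.
- *They were not treated.* They belong to no set, but they were never enrolled, and again 30 were not accrued.

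Every case requires a change to the text of 6.1.

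**Step 2: size of the exclusion.** The inputs are 30 accrued and 3 excluded (SAP 6.1). Then 30 − 3 = 27, and 3/30 = 10.0%. The SAP does not print 27, and it has no sample size calculation to reproduce.

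**Step 3: bounds on the primary endpoint.** The documents report no event counts, so the number of reoperations among the 27, *r*, is an assumption. The 27-subject figure is (27 − r)/27. Restoring the 3 gives (27 − r)/30 if all three were reoperated and (30 − r)/30 if none was.

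| r (assumed) | 27 subjects | 30 subjects, all 3 reoperated | 30 subjects, none of the 3 reoperated | Change (points) |
|---|---|---|---|---|
| 0 | 27/27 = 100% | 27/30 = 90.0% | 30/30 = 100% | −10.0 to 0.0 |
| 2 | 25/27 = 92.6% | 25/30 = 83.3% | 28/30 = 93.3% | −9.3 to +0.7 |
| 4 | 23/27 = 85.2% | 23/30 = 76.7% | 26/30 = 86.7% | −8.5 to +1.5 |
| 8 | 19/27 = 70.4% | 19/30 = 63.3% | 22/30 = 73.3% | −7.0 to +3.0 |

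**Step 4: bounds on a complication rate.** SAP 7.9 specifies Clopper-Pearson intervals for the reoperation proportions, and the same method is used here for illustration. For x events in n subjects, the 95% limits are the 0.025 quantile of Beta(x, n − x + 1) and the 0.975 quantile of Beta(x + 1, n − x). When x = 0 the lower limit is 0 and the upper limit is 1 − 0.025^(1/n).

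- 0/27: upper limit 1 − 0.025^(1/27) = 12.8%
- 0/30: upper limit 1 − 0.025^(1/30) = 11.6%
- 1/30 = 3.3%: limits 0.1% to 17.2%
- 3/30 = 10.0%: limits 2.1% to 26.5%

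A complication type with no events among the 27 could therefore be anything from 0/30 to 3/30 once the excluded subjects are counted.

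**The case against.** The strongest reply uses the second sentence of the Safety Population definition. That sentence refers to enrolled subjects given the protocol-defined repair, and the protocol defines enrolment to include eligibility. If the 3 were ineligible, or their repair was not all-suture, they could fall outside both the Safety Population and protocol 9.1, and a contradiction with those sections would not be certain. This is a fair reading. It does not rescue 6.1, because the same definition then makes the statement that 30 were accrued wrong. The protocol 9.1 conflict depends more on the type of deviation than the Safety Population conflict does.

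A second point concerns the primary endpoint. SAP 7.2 does not itself give 30 for reoperation. It assigns the Safety Population only to disposition, deviations and safety, and the one set it links to the primary variable already removes significant deviations. This is right: the case for 30 in the reoperation analysis rests on protocol 9.1. But SAP 7.2 calls that set supportive and names no main set, which leaves the gap open.

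Third, the bounds are not expected effects. The upper end of the overstatement needs all 3 excluded subjects to have been reoperated. SAP 7.3 and 7.4 use observed cases with known status, so actual denominators may be below 27 or 30 at some visits. Both remarks stand.

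Lastly, the SAP contents list a section on changes from the protocol's methods that is not in the text available for review. It might justify departing from protocol 9.1. It would not by itself reconcile 6.1 with 7.2 and 7.10.

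**Conclusion.** The concern holds, and 6.1 is wrong as written. If the 3 had the protocol-defined repair, removing them from everything contradicts SAP 7.2, SAP 7.10 and protocol 9.1. If any of them did not, or did not meet the enrolment definition, the accrual statement is wrong.

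The certain part of the size is 10% of accrued subjects. The effect on results can only be bounded. For 0 to 8 assumed reoperations among the 27 and complete status on all 30, the reported freedom from reoperation could be 7.0 to 10.0 points too high or 0 to 3.0 points too low. For safety, 0/27 could become as much as 3/30.

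Confidence is highest for the safety and deviation summaries. The protocol 9.1 part is conditional on what the 3 deviations were. No finding is made that the exclusion was driven by outcomes.

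**What to change.** Replace the exclusion sentence in SAP 6.1 with a rule along these lines:

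> Every subject given study treatment remains in the Safety Population for disposition, deviations and safety. Every enrolled subject who had the suture-based repair remains in the protocol 9.1 per-treatment analysis of reoperation and patient-reported outcomes. Significant deviations lead to removal from the supportive Analysis Population only.

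Then:

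- Add the protocol 9.1 set to SAP 7.2 and name it as the set for the primary endpoints.
- List the 3 subjects' deviations, with the reason for exclusion, the treatment received and the date of the decision.
- Report freedom from reoperation at 6 months, 1 year and 2 years with and without the 3.
- If any of the 3 did not have the protocol-defined repair, or did not meet the enrolment definition, correct the count of 30 and say so.

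The cost is new wording in SAP 6.1 and 7.2, one listing, and a small re-run on data that should already exist. The figures may become less favourable.
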